Recruitment and Enrollment. Youth on probation (n=50) in Dutchess and Ulster County probation departments and their primary adult caregivers (n=50) will be recruited through PO referral using the recruitment procedures used in the formative phase. Interested caregivers will be asked to provide written permission and consent for youth and caregiver participation and youth to provide written assent. Although all POs will be involved in proposed study due to randomization at the level of PO, we will recruit POs with active caseloads (n=21) to complete brief assessment using the same recruitment procedures used in the formative phase. Considerable effort will be taken to ensure that youth and caregivers do not feel coerced to participate in Family CONNECT and staff do not feel coerced to complete assessments.

Enrollment and tracking. During Year 1, a participant tracking system will be created using established strategies from our team's prior studies tracking SU youth and JJ-involved families. Data include contact information, 2-3 people who know how to contact them, regular requests for updates, ways to contact while maintaining confidentiality, etc. (Section 5, Human Subjects). We will send thank you notes after each interview,

personalized birthday cards to youth and caregivers if appropriate, and project newsletters. Families will be compensated for participation in accordance with standard remuneration procedures in this population.

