Randomization. We will employ cluster randomization at the level of the PO using a computerized randomization program: 50% of POs at any given site will be assigned to Family CONNECT and 50% to SOC. All caregivers of youth with SU problems based on the MAYS-2 but not currently in treatment will be informed about the study by the PO upon delivery of information that the youth requires SU treatment. Experimental and control manipulations are implemented in the same setting, and thus contamination may be an issue. However, cross-family interactions (e.g., in waiting areas) are not expected to result in significant contamination since families tend to have limited interactions with each other. POs in the experimental arm and Linkage Specialists will be instructed not to assist POs in the SOC arm in any way. POs randomized to SOC may experience decreased morale or a desire to increase performance to match POs in the experimental arm. To offset this, we will clearly articulate to the POs that the study is not an evaluation of their job performance but rather an evaluation of the potential added value that a Linkage Specialist confers with respect to increasing youth enrollment in SU treatment. Despite these precautions some contamination may occur. To identify any possible contamination, we will 1) collect process data from all POs on interactions with Linkage specialists and job satisfaction as part of our implementation assessment (Section 3.3.8.3) and also collect department-wide data on key referral and uptake outcomes for 6 months prior to the implementation of Family CONNECT to identify any changes occurring in the SOC condition (Section 3.3.8.1).

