We chose to randomize at the level of the PO for three reasons: 1) Randomizing by youth would create situations where a PO was working both with youth assigned to Family CONNECT (and Linkage Specialist) and with youth in SOC with considerable contamination potential. 2) Randomizing by site with only two sites is arguably not randomization and would not permit us to separate considerable site effects from differences in the two arms. Although frequency matching of participants would minimize some site effects, the limits to recruitment would be too restrictive in this pilot. Randomizing by site would also give us only limited ability to examine system-level factors that influence implementation of Family CONNECT. 3) Conducting a pre-post design (no randomization) would incur temporal and historical effects (e.g., regression to the mean; changes in services policy), limiting our ability to infer a causal influence of Family CONNECT on our proposed outcomes.

Family CONNECT. Family connect will be adapted using protocols from CONNECT and TIES. In addition, based other successful models of embedded linkage or family support specialists^{78,79}, we will design Family CONNECT to be delivered by POs with a Linkage Specialist who is embedded in the probation department. There will be one Linkage Specialist at each study site who will have prior experience working with families/youth with SU/D problems and/or JJ involvement and hold a Masters degree in clinical social work or a related field. It is anticipated that s/he will assume the linkage and potentially the referral roles of the PO in CONNECT and conduct the engagement strategies originally conducted by a provider in TIES. POs will screen and inform youth and caregivers about any SU treatment needs; POs and Linkage Specialist will work with the research team during the training to develop standard protocols for referring youths to SU treatment and establish formalized relationships with partnering substance abuse treatment agencies.

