Protocol Training. The Drs. [name], [name], and [name] will train the POs and Linkage Specialists in three 1-day workshops. Workshops will review (1) adolescent SU and its correlated risks (e.g., recidivism, common co-occurring disorders), evidence-based treatments, and family role in risk and prevention; (2) how clinicians arrive at a DSM diagnosis, reviewing symptom profiles and criteria for SUD and other related disorders (e.g., PTSD) with substantially elevated prevalence in JJ youth; (3) screening for SU and mental health problems in youth; (4) effective communication techniques with behavioral health providers/agencies, establishing formalized relationships with partnering SU treatment agencies, and developing standard protocols for referring youths to SU treatment; (5) engaging families and youth, identifying barriers to treatment, and increasing motivation to access services; (6) coordinating with SU treatment agencies/clinicians to monitor youth progress and treatment retention. POs will join the first two training workshops, receiving training through topic #4. Linkage Specialists will receive additional training in TIES-derived intensive engagement strategies and monitoring techniques. Knowledge of these topics will be evaluated with pre and post-test training assessments.

Protocol. Following training, the PO and Linkage Specialist will establish memoranda of understanding with community SU treatment agencies. The Linkage Specialist will meet with the youth's PO after study enrollment. After identification of appropriate service agency(ies), the Linkage Specialist will refer the youth to a partnering SU treatment agency and other support services as necessary. S/he will meet with the family at the probation office and/or family's home to complete a family needs assessment and identify facilitators and barriers to treatment. S/he will use adapted TIES strategies to increase treatment motivation, decrease perceived barriers, and develop strategies to overcome practical barriers to attending treatment. The Linkage Specialist will be the liaison among the family, SU treatment provider, and youth's PO, addressing engagement problems with family and/or clinician, tracking youth attendance in treatment and informing the PO, and facilitating communication between the PO and clinician. The Linkage Specialist will track frequency of sessions and contacts and complete standardized process

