Youth SU/D Global Assessment of Individual Needs (GAIN) ¹⁰⁶	Assesses SUD and frequency and quantity of alcohol, marijuana, and other drugs (e.g. cocaine, heroin, ecstasy) over past 30 days, year and lifetime. Well tested diagnostic tool for children and adolescents ¹⁰⁷ .	BL, 2 mos., 6 mos. Youth
Youth recidivism	Count of youth (re)arrests and/or probation violations	2 mos., 6 mos. JJ agency MIS
Demographics	22 items; age, gender, race/ethnicity, family composition/structure, education, parental employment/household income, residential changes educational placement, justice involvement, primary caregiver.	BL, 2 mos., 6 mos. Youth and caregiver

Barriers to treatment Barriers to Treatment Participation Scale ¹⁰⁸	44 items; 4 subscales of barriers to participation: a) stressors and obstacles; b) treatment demands; c) perceived relevance of treatment; d) relationship with therapist. Widely used in services outcome research and validity and reliability well-established ($\alpha=0.94$). ¹⁰⁸	BL, 2 mos., 6 mos. Caregiver
Motivation and perceived SU treatment need Motivation for Youth's Treatment Scale (MYTS) ¹⁰⁹	8 items; assesses intrinsic motivation for treatment with 2 subscales: problem recognition and readiness to participate in treatment. Psychometric properties have been established ($\alpha=0.84-0.89$) ¹⁰⁹	BL, 2 mos., 6 mos. Youth and caregiver
Service utilization GAIN	Prior and current service utilization; type of services; frequency of service use; length of stay	BL, 2 mos., 6 mos. Youth and caregiver
CJS and other system involvement Demographics; GAIN	6-items; assesses number of times youth's caregivers have been in jail or prison; age of youth first and last time Assesses youth removal from home; legal custody of youth	BL, 2 mos., 6 mos. Youth and caregiver
GPM: Family predisposing and enabling factors; youth's SU treatment need		
Caregiver SU/MH problems Beck Depression Inventory ¹¹⁰ State-Trait Anxiety Inventory ^{111,112} Clinical Diagnostic Questionnaire ¹¹³	Depression and Anxiety symptoms, PTSD and Substance Use Disorders. Use of well validated and reliable instruments, widely used in treatment and services research.	BL, 2 mos., 6 mos. Caregiver

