Number of youth enrolled in treatment within the past 6 months is the primary outcome of the service delivery model, assessed at 6-months post baseline. Other linkage and engagement variables that will be examined include: number of youth with SU problems referred for treatment (referral), working alliance between family and PO and family and Linkage Specialist (engagement), and number of youth retained in treatment for at least 4 sessions/6 weeks (retention). Implementation outcomes that will be examined include feasibility, acceptability and potential sustainability. In addition, potential correlates of implementation as specified by the CFIR will be examined, such as organization culture and climate, staff attitudes, agency interconnectedness. Finally, mediators associated with service use that are specified by the GPM model will also be examined, including motivation for treatment, perceived barriers to treatment, caregiver SU problems. As noted in Table 3, this study yields many variables. We, thus, focus on a few of primary interest to illustrate our analytic approach. Attrition and missing data. Based on the PIs K01 award, we anticipate minimal attrition (~15%). We will compare those who did versus did not complete FU on key predictors from the baseline assessment to check for possible bias.

Analysis Plan for Specific Aim 2. Prior to conducting our multivariate analyses, we will examine study

variables using descriptive statistics and test for differences across demographic characteristics (e.g., race/ethnicity, age, education) using t-tests, ANOVAs, and Chi-squares, as appropriate. As participants will be randomized into two groups (at the level of the PO), systematic baseline differences are not expected; however, in the event that some parameters differ across conditions at baseline, they will be included as covariates in subsequent multivariate models. We will calculate descriptive summary statistics corresponding to the study variables at each follow-up (FU) to understand any temporal patterns, as well as compare the two groups in terms of average change from baseline to 6-months post-baseline (averaged across 3 time points).

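### PO-level randomisation does not by itself balance families recruited through arm-aware POs: pre-specify site instead of the imbalance-triggered covariate rule, and tabulate recruitment by PO and arm

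*Combined protocol and SAP*

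**What the plan says.** Allocation is by PO within site (Randomization): "50% of POs at any given site will be assigned to Family CONNECT and 50% to SOC". The same POs bring families in. Under Recruitment and Enrollment, youth and caregivers "will be recruited through PO referral using the recruitment procedures used in the formative phase". Under Randomization, caregivers of eligible youth "will be informed about the study by the PO upon delivery of information that the youth requires SU treatment". Under Family CONNECT, "POs will screen and inform youth and caregivers about any SU treatment needs".

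The Analysis Plan for Specific Aim 2 concludes from PO-level allocation that "systematic baseline differences are not expected; however, in the event that some parameters differ across conditions at baseline, they will be included as covariates" in the later multivariate models. It gives no threshold and no candidate list. The model equation in that section has a generic covariate term, and adjusting for the baseline outcome is offered as an option. No Aim 2 model names site, although the reason given for not randomising by site is that this "would not permit us to separate considerable site effects from differences in the two arms".

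The Primary data analysis overview says that the pilot is not powered for elaborate analysis and aims mainly at sample means and proportions with two-sided 90% intervals.

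**The concern.** There are two separate issues.

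**The inference.** In a cluster design, allocation protects the comparison of individuals only if recruitment within clusters does not depend on arm. Here the randomised unit is also the recruiter and cannot be blind. The Randomization section itself foresees lower morale or extra effort among standard-of-care (SOC) POs, and only POs in the other arm work with a Linkage Specialist. If arm affects whom a PO refers, how the study is presented or who consents, the arms differ from the start. That difference would be mixed into the enrolment comparison. The plan asks for no counts that would show it.

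**The rule.** Adding whatever differs makes the covariate set depend on the baseline data. What an adjusted odds ratio means is then not settled in advance. The factor with the clearest claim to inclusion, the allocation stratum, enters only if it happens to be imbalanced.

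**Working it through.** The documents state no effect size, enrolment rate or sample-size derivation, so there is no figure of the plan's own to reproduce.

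**Inputs from the documents.** 50 youth, about 25 per arm; 21 POs with active caseloads, so 50/21 = 2.4 youth per PO; two sites; POs halved within site; 90% intervals.

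**Assumptions.** The rule is applied as an uncorrected 5% chi-square test between arms; POs split 11/10 over the sites; overall enrolment 40%; no PO-level correlation.

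**1. Can selection be judged?** All youth are screened (Study location and participants), and all caregivers of eligible youth are to be told of the study (Randomization). These steps narrow a PO's discretion over who is approached, but not how the study is put to families or who consents. The order of allocation and recruitment is not stated, and the formative-phase procedures are not reproduced. So a route for selection exists, but its size is unknown.

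**2. Would the rule see a real imbalance?** By exact enumeration at 25 v 25, a 70% v 50% imbalance is flagged 33% of the time and 65% v 50% 22%. Most such imbalances go unflagged.

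**3. How often would site enter?** Simulated allocation within site, with 50 youth spread over the 21 POs:

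| Recruitment per PO | Site flagged | Site omitted | Median site-mix difference |
|---|---|---|---|
| Equal | 6.9% | 93% | 10.1 points |
| Uneven (gamma, shape 2) | 19.9% | 80% | 14.5 points |
| More uneven (gamma, shape 1) | 28.4% | 72% | 17.5 points |

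The site-mix difference moves an unadjusted risk difference by (gap between site rates) × (mix difference):
- Sites at 20% and 60%: 0.4 × 10.1 = 4.0 points to 0.4 × 17.5 = 7.0 points.
- Sites at 30% and 50%: 0.2 × 10.1 = 2.0 points to 0.2 × 17.5 = 3.5 points.

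This is chance error, not bias.

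**4. What does naming site gain in precision?** Ideal formula: half-width = 1.645 × √(2v/25).
- Site ignored: v = 0.4 × 0.6 = 0.24, giving 22.8 points.
- Within sites at 20/60: v = (0.16 + 0.24)/2 = 0.20, giving 20.8.
- Within sites at 30/50: v = (0.21 + 0.25)/2 = 0.23, giving 22.3.

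The formula ignores unequal arms and the cost of the extra term, so it flatters adjustment. Simulation with equal recruitment gives about 23.1 to 21.2 at 20/60, about 23.3 to 23.0 at 30/50, and 23.0 to 23.2 (slightly worse) at 37/43.

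**5. Would fixed covariates repair selection?** Suppose motivated youth enrol at 60%, others at 20%, and 70% v 50% of the arms are motivated. The bias is 0.70 × 0.6 + 0.30 × 0.2 − 0.40 = 0.08, or 8 points. In simulation, a baseline marker of motivation that is 65% accurate leaves 7.4 points if always included and 7.8 under the triggered rule. At 60% accuracy these are 7.6 and 7.8. Near-complete removal appears only if the selecting factor itself is measured.

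**6. Scale.** If SOC enrolment is 20% and 60% at equal-sized sites, a site-adjusted odds ratio of 3 gives 42.9% and 81.8%, mean 62.3%. The unadjusted odds ratio is (0.623/0.377)/(0.4/0.6) = 2.48. At 30/50 it is 2.86.

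**The case against.** The strongest reply is that this is an unpowered estimation pilot. Its leading outputs are sample proportions with intervals, and the covariate rule does not touch those. That is correct, and it limits the rule's harm to the adjusted models. It does not answer the selection issue, which would reach the unadjusted proportions too.

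Second, the 5% between-arm test is only one reading. The sentence on t-tests, ANOVAs and chi-squares may describe comparisons across demographic groups, and the sentence containing the rule names no test. This stands, so the flag rates are illustrative. A reader might also infer that chance flags would be common because Table 1 lists "22 items; age, gender, race/ethnicity, family composition/structure, education, parental employment/household income" and more. The documents do not say that each item would be tested between arms, so no weight is placed on that.

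Third, site is balanced in expectation by design, and the passage on site effects explains why site was rejected as the unit of randomisation. True: what is lost by omitting site is precision and a fixed model, not unbiasedness.

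Fourth, the plan has partial safeguards: six months of department-wide referral and uptake data before implementation, and agency-system sources for several outcomes. These provide some check, but they are not counts of who was eligible, informed and consented by PO and arm. The plan also says only that differences are not expected, and it provides for them if they occur.

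Three stronger readings should be resisted. A reader might infer that selection will bias the enrolment difference by several points; the 8-point figure rests wholly on assumed rates. A reader might infer that fixed covariates would cure selection; step 5 shows that a plausible marker removes almost none. A reader might infer that the MAYSI-2 score should be a compulsory covariate. Nothing in the documents says that it predicts enrolment, inclusion restricts its range, and POs who know their arm may be the ones screening.

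**Conclusion.** The concern holds in a limited form. The inference from PO-level randomisation to no expected systematic differences is not valid when arm-aware POs recruit, although the size of any selection cannot be judged from the documents. The imbalance-triggered rule leaves the adjusted Aim 2 models unfixed. If run as a 5% test, it would leave out the allocation stratum in about 72% to 93% of trials.

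The sure gain from naming site is a model settled before the data are seen. The precision gain ranges from about 2 points of half-width (sites at 20/60) through about 0.3 (30/50) to a slight loss when the sites barely differ. These figures rest on the assumed site rates, the 11/10 PO split, equal recruitment and no PO-level correlation. The change is worth making because it costs little, not because the present plan is shown to be biased.

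**What to change.** 1. Delete the imbalance-triggered rule. Pre-specify site in every Aim 2 between-arm model, and make adjustment for the baseline value the rule for scale outcomes. Baseline enrolment in treatment should vary little, since regular attenders are excluded, so adjusting for it would add little to the primary outcome. Report unadjusted proportions and risk differences alongside. Do not add a compulsory MAYSI-2 term.
2. Replace the statement on baseline differences with, for example: *Recruitment by unblinded POs may produce selection between arms, which covariate adjustment cannot be relied on to remove.*
3. Tabulate eligible, informed and consenting families by PO and arm, so that selection can be seen. The larger trial will need these counts too.

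Cost: some wording, one count table and one degree of freedom for site in a model of 50 youth. Adjusted and unadjusted odds ratios must be labelled separately and not compared directly. If the sites turn out to be alike, the site term widens the interval by about 0.2 points (23.0 to 23.2 in step 4).

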
Domain 1 (enrollment and retention outcomes): Differences between youth involved in Family CONNECT and those in the SOC comparison condition with respect to the following variables at 2- and 6-months post baseline: a) youth who began SU treatment (y/n) (completed intake + attended 1 session); b) youth who attended 4 sessions/remained in treatment for 6 weeks (y/n); c) total number of SU treatment sessions attended.

Domain 2 (cross-system referral and engagement outcomes): Differences between youth and families involved in Family CONNECT and those in the SOC comparison condition with respect to the following variables at 2- and 6-months post baseline: a) youth referred to SU treatment (y/n); b) youth/caregiver engagement.

Domain 3 (secondary outcomes): Differences between youth and families involved in Family CONNECT and those in the SOC comparison condition with respect to the following variables at 2 and 6 months post-baseline: a) youth (re)arrest (y/n); youth probation violation (y/n); c) any SU (y/n) and d) frequency of SU in past 30-days

Analysis Plan for Specific Aim 3. Using our theoretically informed model (see Figure 1) as a blueprint¹²⁶, we will use SEM to begin to unpack what theoretical constructs and pathways were influential in the intervention, and aid us to refine our conceptual model for the larger RCT. For example, it is possible that Family CONNECT will have more positive effect on service referral and engagement outcomes when operating in a probation department that is more supportive innovative concepts. Here, organizational culture would appear to modify the impact of Family CONNECT on youth service referral and engagement outcomes. We will examine the Lagrange Multiplier and Wald Tests to consider the deletion or inclusion of paths¹²⁷; ultimately, however, the deletion or inclusion of paths will be informed by theoretical underpinnings. Once the model is identified, we will test for group differences between intervention conditions in latent constructs and in the proposed paths between these constructs. This method will allow us to estimate the intervention effects on the constructs directly as well as their relationships to one another.¹²⁸ We will use three goodness-of-fit indices: Bentler-Bonnet's Normed Fit Index, Bentler-Bonnet's Non-Normed Fit Index, and the Comparative Fit Index. We will also verify the root mean-square error of approximation (RMSEA) as an index of misfit. Well-fitting models will have fit indices of .90 or higher and <.06 for RMSEA.

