Family Engagement, Cross-System Linkage to Substance Use Treatment for Juvenile Probationers -- Phase 3

NCT03048552

Study Protocol

1/1/2016

Study Protocol

Study Aims. Working with two county probation departments that have adolescent SU services, we propose the following Specific Aims:

1. To examine, in a pilot-test, the impact of Family CONNECT on improving (i) cross-system (probation-SU agency) referral; (ii) family engagement; (iii) enrollment and retention of youth/families in SU treatment; and (iv) secondary outcomes of reducing youth SU and recidivism.
3. To elucidate multi-level factors (e.g., family, staff, and organizational-level) that influence implementation of Family CONNECT in probation settings to inform a larger trial.

Overview of study design. We propose to pilot-test a service delivery model for youth on probation that targets probation-, treatment system- and family-level factors to increase uptake of SU services; and to understand the organizational elements required to successfully implement this adapted model in juvenile probation settings (see Timeline in Budget Justification). Guided by the CFIR framework and GPM, **Pilot Test and Implementation Evaluation**, youth on probation (n=50) and their caregivers (n=50) will participate in a pilot of Family CONNECT to examine its preliminary impact on cross-systems referral, family engagement, and retention of youth/families in SU treatment. We will explore family-, staff-, and organizational-level factors that influence Family CONNECT feasibility, acceptability, and sustainability in probation settings (Year 2; Year 3, Months 1-6). Youth-caregiver dyads will be randomized at the level of probation officer (PO) to Family CONNECT or standard of care (SOC). Youth and caregivers will be assessed at baseline, and 2 and 6 months post-baseline. Probation staff will be assessed before implementation of Family CONNECT and at 6, 12 and 18 months post-training.

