Family conflict/support Family Environment Scale ¹¹⁴ Caregiver Strain Questionnaire-Short form ¹¹⁵	18 items; assess family functioning: cohesion and conflict. Well validated, used with delinquent youth ($\alpha=0.61-0.78$). ^{114,116,117} 7-items; assess strain caregiver experiences providing for a youth with behavioral health needs. Subscales =objective & internalized strain; validity and reliability well-established ($\alpha=0.82-0.90$) ¹¹⁸	BL, 2 mos., 6 mos. Youth and caregiver BL, 2 mos., 6 mos. Caregiver
CFIR: Inner setting and characteristics of individuals		
Organizational and staff characteristics National Criminal Justice Treatment Practices (NCJTP) survey ¹¹⁹	1) mission and goals of correctional programs; 2) organizational climate and culture for providing services; 3) organizational capacity and needs; 4) opinions of administrators, staff regarding rehabilitation, punishment, and services provided to offenders; 5) treatment policies and procedures; and 6) working relationships between correctional and other agencies. Psychometric properties established ¹¹⁹	Pre-implementation; 6, 12- and 18-mos. post-training Staff and Linkage Specialist

Data Management and Analysis.

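### The Aim 3 example of departmental culture modifying the effect of Family CONNECT cannot be identified with two departments, because culture, county and Linkage Specialist share one contrast

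*Combined protocol and SAP*

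**What the plan says.** Under Study Aims, Aim 3 is "To elucidate multi-level factors (e.g., family, staff, and organizational-level) that influence implementation of Family CONNECT in probation settings to inform a larger trial". The Analysis Plan for Specific Aim 3 uses SEM, built on the conceptual model in Figure 1, as a first look at which constructs and pathways mattered. The results are to help refine that model for the larger trial. The section has one worked example: the intervention may do more for referral and engagement in a department that is more receptive to new ideas. It reads such a finding as "organizational culture would appear to modify the impact of Family CONNECT on youth service referral and engagement outcomes". It then plans to test whether paths between constructs differ by arm.

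The relevant design facts are:

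- Departments (Study Aims): "Working with two county probation departments that have adolescent SU services".
- Specialists (Family CONNECT section): "There will be one Linkage Specialist at each study site".
- Allocation (Randomization): "50% of POs at any given site will be assigned to Family CONNECT and 50% to SOC". Specialists are told not to help POs in the standard-of-care (SOC) arm.
- Site effects: among the reasons for randomising by PO, the plan says that randomising two sites "would not permit us to separate considerable site effects from differences in the two arms". It adds that site randomisation would limit the study of system-level factors, which implies that PO randomisation does better.
- Measurement (Table 1, inner setting): climate and culture come from the National Criminal Justice Treatment Practices (NCJTP) survey, answered by staff and Linkage Specialists, at "Pre-implementation; 6, 12- and 18-mos. post-training".

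**The concern.** A modifier that belongs to the department can take only two values here. Its interaction with arm is therefore one number: the Family CONNECT effect in one county minus the effect in the other. Differences in county, agency supply, caseload mix or the skill of the single specialist would produce the same number. The plan recognises the two-site problem when it rejects site randomisation, but does not carry it over to modifiers. Randomising POs within each site makes the arm effect estimable in each county. It does not explain why the two effects differ.

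What is at stake is what the pilot may conclude about departments. If the example is followed as written, a county or specialist difference could be labelled organisational culture and enter the conceptual model for the next trial.

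**Working it through.** The documents give no sample size, power or effect size for Aim 3, so there is no figure to reproduce. The check is of identifiability.

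**Inputs.** Departments D = 2 (Study Aims). One specialist per department (Family CONNECT). POs split 1:1 within site (Randomization). 21 POs with active caseloads and 50 dyads (Recruitment and Enrollment). Two-sided 90% intervals (Primary data analysis overview).

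**Step 1: aliasing.** Let d = 0 or 1 for department and A = 0 or 1 for arm. Any departmental culture score can be written c = c0 + (c1 − c0)d. Then A×c = c0·A + (c1 − c0)·A×d. So culture is an exact function of department, and arm-by-culture is an exact function of arm and arm-by-department. In the SEM, the culture path within an arm is the county difference in that arm, rescaled. Comparing that path between arms gives the arm-by-county contrast again.

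**Step 2: specialist.** Each site has one specialist, who serves only the Family CONNECT arm. A difference between specialists therefore enters as A×d, the same term.

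**Step 3: rank.** The columns are [1, A, d, A×d, c, A×c], with 21 POs split 11 and 10 between departments (an assumption) and about 1:1 by arm within each. The rank is 4 of 6 at N = 50, 500, 5,000 and 50,000 dyads. Across department-specific effects, a culture slope has D − 2 residual degrees of freedom: 0 with 2 departments, 1 with 3, 8 with 10, 18 with 20. Only more departments help.

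**Step 4: what happens if department is left out.** The columns [1, A, c, A×c] have full rank (4 of 4), so the software returns an estimate, but it is the county contrast under another name. To illustrate, suppose there is no culture effect, the outcome SD is 1, the four cells are equal and there is no PO clustering. The contrast then has sampling variance 4 × 1/(N/4) = 16/N. Let department or specialist effects have SD τ. The documents give no value for τ, so it is an assumption. The total variance is 16/N + 2τ², and the chance of a false culture finding is 2[1 − Φ(z·√(16/N)/√(16/N + 2τ²))].

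For N = 50 and τ = 0.3: √0.32 = 0.566 and √(0.32 + 0.18) = 0.707. At nominal 0.05, z × ratio = 1.96 × 0.80 = 1.57, giving 12%.

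| N | nominal 0.05, τ = 0.3 | nominal 0.10 (90% interval), τ = 0.3 |
|---|---|---|
| 50 | 12% | 19% |
| 500 | 45% | 52% |
| 5,000 | 80% | 83% |
| 50,000 | 93% | 95% |

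Over τ = 0.1 to 0.5 at nominal 0.05, the range is 6–22% at N = 50 and 81–96% at N = 50,000. With τ = 0 the rate stays at its nominal level. More dyads make the wrong label more likely, not less.

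**Step 5: a PO-level score.** If c is each PO's own score and varies within department, the same six-column model has rank 6 of 6. That is a different quantity (perceived culture), and it varies at PO level. With 21 POs and 6 terms, at most 21 − 6 = 15 degrees of freedom remain between POs.

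**The case against.** The strongest reply is that the section promises very little. The culture case is introduced as a possibility, inside an exploratory SEM, and is not a named hypothesis or a specified model term. That stands. A reader might infer that the plan sets out to show that culture modifies the effect; the text does not commit to that.

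A reader might also infer that the whole organisational part of Aim 3 fails. The documents do not support that either. The data analysis overview treats culture, climate and staff attitudes as possible correlates of implementation outcomes, and the aliasing does not reach staff-level correlates. Nor does any section say that post-training culture scores will be used as modifiers. A pre-implementation wave exists, and the plan leaves the choice of wave open.

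It can further be said that individual staff answer the NCJTP and that the plan never says scores will be averaged by department. Figure 1, which might settle the level, is not in the text available for this review. That is fair, but the example itself speaks of a more supportive department, so the department reading is the natural one and the PO-level alternative is nowhere specified.

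The admission of low power is not an answer. Low power can be cured by more data of the same kind, and aliasing cannot.

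**Conclusion.** The point holds for the example as worded, at department level. There is one contrast, 0 residual degrees of freedom and rank 4 of 6 at any number of dyads, so culture, county, local agencies and specialist cannot be told apart. This rests only on two departments, one specialist at each, and a culture score defined per department. The false-positive rates rest on an assumed τ and a simplified variance. They show direction and are not needed for the conclusion. The primary outcome, the arm comparison, and the staff-level and implementation-outcome parts of Aim 3 are untouched. What must change is what the pilot may conclude about departmental culture as a modifier.

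**What to change.** In the Analysis Plan for Specific Aim 3:

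1. Replace the department-level moderation example with a descriptive report. Show NCJTP and Program Sustainability Assessment Tool (PSAT) profiles for each department beside the department-specific arm differences. State that culture, county and specialist cannot be separated with two departments.
2. If culture is examined as a modifier, define it as each PO's own pre-implementation NCJTP score and call it a staff-level perception. Include department and arm-by-department as fixed effects, so that the comparison is between POs within department. Label it exploratory, because only about 21 POs inform it.

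The cost is wording; the data are already to be collected. The downside is that the departmental culture claim becomes descriptive, and testing it is left to a larger trial with more departments.
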